6.2.12 Follow-Up Visits 1 and 2 (Week 12 and Week 26)

During Follow-Up Visits 1 and 2 (Duration: ~30 minutes) participants will:

1. Perform a CO breath assessment or provide a urine sample for a cotinine assessment, answer combustible marijuana items, and complete a concomitant medication review.
2. Provide daily smoking rate (timeline follow back [TLFB]).
3. Have weight measured.
4. Complete paper and pencil questionnaires:
 - Adverse Events Form (Open-Ended AEs)
 - Physical Activity (PAR)
5. If a participant reports not smoking (not even a puff of a cigarette) for at least the 7 days prior to the Follow-Up Visit without the aid of NRT, the participant will be asked to provide a 5ml saliva sample used to assess cotinine levels and verify abstinence from smoking.
6. Confirm the 24-hour dietary recall (Week 12 [#4] and Week 26 [#5]) schedule.

6.2.13 fMRI Scan Visits 1 & 2 (~Week -2 and ~Week 7-8)

Participants who are both eligible and elect to participate in the neuroimaging sub-study will complete two neuroimaging sessions: Scan 1 will occur prior to the Baseline Visit (~week -2) and Scan 2 will occur during the final week of nicotine patch therapy (~week 7-8). Prior to each scan, participants will be instructed to fast overnight (beginning at ~10pm) until after the

CONFIDENTIAL

This material is the property of the University of Pennsylvania. Do not disclose or use except as authorized in writing by the study sponsor

completion of their fMRI scanning visit the following day. The fast period does not include a Boost® Nutritional Drink (Vanilla) that will be provided during the scanning visit to standardize prior food intake and remove deprivation to increase sensitivity to changes in food reward. Since participants are asked to fast overnight, all scanning sessions will be scheduled to occur in the morning. However, a scan may be completed in the afternoon at the discretion of the Principal Investigator due to extenuating circumstances. Additionally, participants will be instructed not to consume caffeine for 4 hours prior to the beginning of the visit in order to standardize satiety. Including the 1-hour fMRI scan, scanning visits are expected to last ~3 hours in duration. If a scanner hardware/software malfunction occurs and data is unable to be collected, an fMRI scan(s) may be rescheduled at the discretion of the Principal Investigator.

At both scanning visits participants will:

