6.5.2 Screening/Covariates

Urine Drug Screen: A urine sample (~20-30ml) will be collected at the Intake Visit and both neuroimaging scans (neuroimaging sub-study only) to conduct a urine drug screen. The urine drug screen indicates whether the subject has recently taken any of the following recreational drugs or medications: THC, cocaine, opiates, amphetamines, methamphetamines, phencyclidine (PCP), ecstasy (MDMA), barbiturates, benzodiazepines, methadone, tricyclic antidepressants, and/or oxycodone. Participants with a positive urine drug screen for any substance listed above other than THC or tricyclic antidepressants at the Intake visit will be deemed ineligible. A urine sample that doesn't register a temperature reading of at least 90 degrees Fahrenheit will not be considered a valid sample. In an effort to remain CLIA-compliant, results from urine drug screen will not be shared with participants. Participants will be informed that the testing is for research purposes only and that they will be informed of their eligibility status, but not of the specific testing results. In order to document inclusion/exclusion criteria for regulatory purposes, results of the urine drug screens (test cup) will be retained in research charts and in an electronic research record within our local data management system (Access). These results are not and will not be entered into a participant's electronic medical record.

Participants who test positive for any study-prohibited medications/recreational drugs at either neuroimaging scan (neuroimaging sub-study only) will not be permitted to complete the neuroimaging sub-study and may be deemed ineligible for the main study at the discretion of the Principal Investigator.

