Combustible Marijuana Items: Participants will be asked if they smoked combustible marijuana in the past 24 hours. If yes, the participant will be asked how many hours ago they last used. Information collected on combustible marijuana may be considered a confounding variable during data analysis in relation to CO level.

Concomitant Medications: At the Intake Visit, participants will be asked to list all medications (prescription or non-prescription) and NRTs currently taken and/or recently discontinued (within the past 14 days) as a baseline collection. All information will be collected on a Concomitant Medication Log that will be maintained within the participant's study chart. At every subsequent in-person visit, participants will be asked if they have taken any additional medications (prescription or non-prescription), NRTs, and/or changed the dosage or stopped taking any previously reported medications since their last in-person visit. Participants who report taking contraindicated medication(s) over the course of the study period may only remain eligible if the Study Physician and/or Principal Investigator determine that the contraindicated medication(s) did not impact the study design, data quality, and/or participant safety and welfare.

CONFIDENTIAL

This material is the property of the University of Pennsylvania. Do not disclose or use except as authorized in writing by the study sponsor

Antibiotics Form: Participants who are participating in the microbiome sub-study will be asked about their antibiotic use over the past six months at the Baseline Visit.

Yogurt and Pro/Prebiotic Form: Participants who are participating in the microbiome sub-study will be asked about their consumption of yogurt and pro/prebiotics use over the past four weeks at the Baseline Visit (wk-2), Mid-Tx. 3 Visit (wk4), and End of Treatment Visit (wk8).

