6.5.6 Outcomes

Weight: Weight (primary outcome) will be measured by a physician's scale (pounds) at the beginning of every in-person visit. Participants will be wearing light clothing without shoes. Pre-cessation weight will be computed as the average of weights at the Intake and Baseline Visits prior to any change in smoking behavior. Weight change from Baseline to the 26-week follow-up will serve as a primary weight outcome variable.

Food Intake (24-Hour Dietary Recalls): Food intake (secondary outcome) will be assessed via 3 telephone-administered, 24-hour dietary recalls during the week after (or near) the Baseline, Mid-Treatment 3 (week 4), End of Treatment (week 8) and the 12-week and 26-week follow-up visits (n=15). A trained member of the research staff will use a multi-pass method with an interactive computerized software program, the ASA24® (Automated Self-Administered 24-hour Recall), to determine total kcal/day (outcome variable). The ASA24® was created by investigators at the NCI. Three recalls are considered optimal for assessing dietary intake, especially when weekend and weekdays are assessed, as we propose to do when possible. If participants are unable to complete a scheduled recall over the telephone or are onsite for a scheduled visit, participants may be asked to complete a 24-hour dietary recall with the research staff in-Center. Comparable accuracy can be achieved when administered in-person and over the telephone. Food recalls are widely used, reliable and valid, assessing kcals/day within 10% of actual dietary intake measured under laboratory observation and by doubly labeled water.

Changes in food intake (kcals) from baseline to week 12 will serve as an outcome for the microbiome sub-study.

Smoking Cessation (CO, Urine Cotinine, and Saliva Cotinine): Smoking abstinence (primary outcome) will be assessed and biochemically verified at EOT (week 8), at 12 and 26 weeks after the target quit date. The primary smoking outcome variable will be 7-day point prevalence abstinence (no smoking, not even a puff, for at least 7 days prior to the assessment) biochemically verified by CO < 5 ppm or Urine Cotinine assessment at a sensitivity of 100 ng/mL at EOT (week 8) and Follow-Up 1 and 2 visits (Week 12 and Week 26). Smoking status will also be biochemically confirmed by saliva cotinine < 15ng/ml at the 12- and 26-week follow-up.

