6.7 Sample Size Determination- Parent (Main) Study

For **Aim 1** we hypothesize that BAS+ vs. SC will have higher smoking abstinence rates and less PCWG at the 26-week follow-up (primary outcomes). Power calculations were all approximated as t-tests or z-tests, and conducted using PASS Software (Power and Sample Size, NCSS Software, Kaysville, UT), Bonferroni corrected for two primary outcomes ($p=.025$). Proportions of abstinent and smoking subjects will be compared using the log of the odds-ratio, which has a known variance. Informed by smoking cessation counseling plus TN research, we anticipate that the 6-month abstinence rate will be 13% in the SC (control) group and 25% in the BAS+ group (consistent with a persistent effect of BAS+ after the discontinuation of TN). A sample of 213 per group provides 82% power to detect this 12% difference in quit rates at 6 months. This represents a clinically meaningful effect and corresponds to a small effect size ($\delta=.15$). For PCWG, we will include all participants in the analysis, while testing a smoking status x treatment interaction. Informed by epidemiological and clinical studies of PCWG, we will have 80% power to detect a 6 pound (2.72 kg) difference in PCWG between BAS+ and SC, using the interaction term. We expect BAS+ vs. SC will have less post-cessation food intake (secondary outcome) at the 26-week follow-up. We have 80% power to detect a 320 kcal/day difference between the two groups ($p = .05$). In light of these considerations (i.e., 213 subjects per arm; total 426) and an attrition estimate of 15% across accrual, we will recruit a total of 245 subjects to each arm for a total of 490 subjects (~500).

For **Aim 2**, we hypothesize that BAS+ vs. SC, will increase alternative reinforcers, and reduce food reward, the RRVF, and food cue-induced craving. These changes, in turn, will predict less food intake and PCWG, and greater smoking abstinence at the 26-week follow-up. Using structural equation modeling, we will test the treatment effect on the slope of the mediators versus time, with pre-quit values representing the intercepts. We will examine the proportion of

CONFIDENTIAL

This material is the property of the University of Pennsylvania. Do not disclose or use except as authorized in writing by the study sponsor

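### A cigarette abstainer who smokes marijuana can fail the CO check; no rule lets cotinine settle the case, and treating marijuana as a confounder does not correct the outcome

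*Combined protocol and SAP*

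**What the plan says.** Four parts of the protocol bear on this.

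- **Entry.** Under Urine Drug Screen, Section 6.5.2 makes ineligible anyone with a "positive urine drug screen for any substance listed above other than THC or tricyclic antidepressants" at intake. A THC-positive result alone does not exclude. Section 4.6 separately excludes a history of substance abuse in the past 12 months.
- **Outcome.** In Section 6.5.6, 7-day point prevalence abstinence is "biochemically verified by CO < 5 ppm or Urine Cotinine assessment at a sensitivity of 100 ng/mL at EOT (week 8" and at the two follow-up visits. Under Urine Cotinine Test, Section 6.5.2 presents the urine test as the means of confirming smoking status until CO readings can safely resume.
- **Saliva.** At weeks 12 and 26, Section 6.2.12 says that for self-reported 7-day abstainers not using NRT "the participant will be asked to provide a 5ml saliva sample used to assess cotinine levels and verify abstinence from smoking". Section 6.5.6 adds that status will *also* be confirmed by saliva cotinine below 15 ng/mL.
- **Marijuana.** Use in the past 24 hours, and hours since last use, are recorded. The stated purpose is that "Information collected on combustible marijuana may be considered a confounding variable during data analysis in relation to CO level". Section 6.10 does not name marijuana in the primary model, which takes in covariates found to be related to the outcome in preliminary analyses.

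No section says how to classify a self-reported abstainer with CO of 5 ppm or more, recent marijuana use and negative cotinine, or which marker prevails when they disagree.

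**The concern.** The protocol identifies something other than cigarettes that bears on CO, admits people exposed to it, and keeps CO as the verifying test while CO is in use. The consequence is an error in the outcome, not confounding: a person who has not smoked a cigarette for 7 days may go unverified. Entering marijuana as a covariate does not change how that person is coded.

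The item is also measured after randomisation. If treatment changes marijuana use, adjusting for it can itself bias the comparison. And because marijuana would be related to the outcome partly by corrupting it, selecting covariates on preliminary association could bring it into the model for the wrong reason.

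The endpoint is also inconsistent over time. The same behaviour can leave a participant unverified while CO is in force and verified abstinent while urine cotinine replaces it.

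**Working it through.** **Inputs from Section 6.7.** The plan states: "we anticipate that the 6-month abstinence rate will be 13% in the SC (control) group and 25% in the BAS+ group". Alpha is 0.025 after the Bonferroni correction for two primary outcomes. The plan adds: "A sample of 213 per group provides 82% power to detect this 12% difference in quit rates at 6 months". On the test: "Proportions of abstinent and smoking subjects will be compared using the log of the odds-ratio". Sidedness is not stated for the parent study.

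**Reproducing the plan's power** (two-sided 0.025, critical value 2.241):

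- Pooled z: null SE = √(2 × 0.19 × 0.81 / 213) = 0.0380; alternative SE = √((0.13 × 0.87 + 0.25 × 0.75) / 213) = 0.0376. Power = Φ[(0.12 − 2.241 × 0.0380) / 0.0376] = 82.3%.
- Log odds ratio: OR = (0.25/0.75) / (0.13/0.87) = 2.231, log 0.802; SE = √(1/27.69 + 1/185.31 + 1/53.25 + 1/159.75) = 0.258. Power = Φ(0.802/0.258 − 2.241) = 80.8%.

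Both are close to the stated 82%. One-sided 0.025 gives 88.7% (pooled z) and does not reproduce it.

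**Equal misclassification.** Let m be the share of true abstainers left unverified because of marijuana and then analysed as not abstinent. Observed rate = true rate × (1 − m). The documents give no value for m; 5–20% is an assumption.

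| m | SC | BAS+ | Difference (points) | OR | Power, pooled z | Power, log OR |
|---|---|---|---|---|---|---|
| 0 | 13.0% | 25.0% | 12.0 | 2.23 | 82.3% | 80.8% |
| 5% | 12.35% | 23.75% | 11.4 | 2.21 | 79.6% | 78.0% |
| 10% | 11.7% | 22.5% | 10.8 | 2.19 | 76.6% | 75.0% |
| 20% | 10.4% | 20.0% | 9.6 | 2.15 | 69.9% | 68.3% |

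In people: the expected true abstainers number 213 × 0.13 + 213 × 0.25 = 80.9, so the range is about 4 (5%) to 16 (20%) participants.

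Section 4.2 now targets about 340 randomised. At 170 per arm the pooled-z power is 72.1% with m = 0, 65.8% at 10% and 58.9% at 20%.

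**Unequal misclassification** (213 per arm, pooled z):

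- 10% in SC and 20% in BAS+: 11.7% vs 20.0%, OR 1.89, power 54.2%.
- 20% in SC and 10% in BAS+: 10.4% vs 22.5%, OR 2.50, an overstatement.

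**What a covariate achieves.** Take marijuana use as equal in both arms, with 98% of true abstainers among users failing CO. Fit a logistic regression to expected counts, with and without a marijuana term.

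- 10% use: observed rates 0.13 × (1 − 0.098) = 11.7% and 0.25 × (1 − 0.098) = 22.6%. OR 2.19 unadjusted, 2.23 adjusted; power 75.1% and 76.2%.
- 20% use: observed rates 10.5% and 20.1%. OR 2.16 unadjusted, 2.23 adjusted; power 68.6% and 70.7%.

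With balanced use, adjustment returns the odds ratio to about its true value. The abstinence rates stay too low, and only one or two points of power come back.

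**The case against.** A reader might infer that these participants fail CO and are scored as smokers. The documents do not say so. The only explicit rule for counting people as smokers, in Section 4.2, covers loss to follow-up. Sections 3.1 and 6.5.6 join CO and urine cotinine with *or*, and saliva cotinine is taken at the primary time point. This stands as a limit on the claim, which is that such a person *can* read 5 ppm or more and be left unverified. It does not close the gap: Section 6.5.2 presents urine cotinine as the substitute while CO is suspended, and *also* in Section 6.5.6 can be read as a further requirement.

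The marijuana sentence may mean only that individual CO readings will be interpreted in its light. That is possible, and recording hours since use fits it, but no rule for doing so is given.

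A reader might also infer that adjustment is useless, or that BAS+ will be disadvantaged because it promotes substitute rewards. Neither is supported. Adjustment nearly restores the odds ratio when use is balanced. Section 6.5.1 directs BAS+ towards activities not associated with smoking, so the direction of any imbalance is unknown.

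Finally, 20% of true abstainers may be extreme. Failing CO would require use recent and heavy enough to matter, and the substance-abuse exclusion should remove some heavier users. Under equal misclassification the odds ratio barely moves and the risk ratio does not move at all. These points stand.

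**Conclusion.** The concern holds as a gap in outcome classification with an unsuitable stated remedy. As written, the CO rule can leave a true cigarette abstainer unverified at weeks 12 and 26, and the covariate does not correct this.

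The size cannot be established from the documents. Under the assumed 5–20% and equal effect in both arms, the main cost is power: roughly 2 to 3 points at the low end and 12 to 13 at the high end, at 213 per arm. Abstinence rates are understated in proportion, and the odds ratio falls only slightly. Bias of any consequence needs unequal misclassification, for which there is no evidence in either direction. The unequal scenarios illustrate sensitivity and are not forecasts. The point merits correction mainly because the samples needed at the primary time point are already collected.

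**What to change.** - **Section 6.5.6:** state that at weeks 12 and 26 a participant who reports 7-day cigarette abstinence, reports combustible marijuana in the past 24 hours and has CO of 5 ppm or more is classified by saliva cotinine, with below 15 ng/mL counted as abstinent.
- **Section 6.5.2:** replace the confounding-variable sentence with a reference to that rule, so that the problem stays acknowledged.
- **End of treatment:** no saliva is taken and patch treatment has just ended, so cotinine is a weak arbiter. Keep all randomised participants and report a sensitivity analysis coding these cases first as smoking, then as abstinent. Dropping them would remove randomised people because of a post-randomisation behaviour.

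The cost is one rule and one sensitivity analysis, with no new data. Section 6.5.2 describes cotinine as a product of nicotine metabolism, so it can separate marijuana from cigarettes only where there is no other nicotine source. Participants using NRT, or mixing marijuana with tobacco, cannot be resolved this way and stay under the current rule. The rule also depends on a self-report of marijuana use, but that report only opens the route; the saliva result decides.

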6.5.3 Moderators

Weight Concerns: Weight concerns associated with quitting smoking will be measured with a reliable ($\alpha=.87$) and valid 6-item scale. Responses to the 6 items range from 1 (not at all) to 10 (very much). Scores are the average of responses to all items.

Depression Symptoms (CES-D): The Center for Epidemiologic Studies Depression Scale is a 20-item Likert-style scale used to assess depressive symptomatology. This scale has high internal consistency ($r=.85-.90$) and has been shown to correlate with clinical ratings of the severity of depression. In our previous research, CES-D scores have correlated significantly with self-medication smoking and nicotine dependence.

Gender: Gender (self-identification) will be assessed via self-report during the initial telephone screen and reconfirmed in-person at the Intake Visit.

6.5.4 Mechanisms

Individualized Food (Pre-FCQ-S): In preparation for the food cue-induced craving task, participants will rate how appetizing they find pictures of food (e.g., cupcakes, fruits, vegetables) at the Intake Visit. Foods rated least appetizing ($n=20$) and foods rated most appetizing ($n=20$) will be selected to create personalized food cue stimuli.

Preferred Snack Choice (Pre-RRVF): Participants will select either the salty (Lay's® Classic potato chips) or sweet (M&M's®) snack food as the snack to "work for" when completing the RRVF task over the remainder of the study.

Food Cue-Induced Craving (FCQ-S): Food cue-induced craving will be assessed using a personalized food cue exposure paradigm, whereby pictures of foods rated least appetizing (L, $n=20$), most appetizing (M, $n=20$), and a picture of a glass of water (W, $n=20$) will be presented to participants seated at a computer screen. Participants will be instructed to imagine tasting and eating the pictured food for as long as the image is presented. The images will be presented in six blocks. Each block consists of image presentation (10 images, 8 sec duration) and craving assessment. The M, L, and W food cues will be presented in one of two sequences (i.e., MWLMWL or LWMLWM) counterbalanced across participants. Before the task and after each block, participants will complete the state version of the Food Craving Questionnaire, Desire Subscale (FCQ-S). The 3 items (desire to eat, craving, urge to eat) will be tailored to ask about the M, L, and W images on a 5-point scale (strongly disagree to strongly agree). Personalized cues can maximize craving induction and produce greater increases in subjective craving and objective indices of cue reactivity than standard cues. Reactivity to palatable food images is associated with body mass and weight gain. The Food Cue-Induced Craving task will be administered at the Baseline (Week -2), Mid.-Tx 1 (Week 1), Mid.-Tx 3 (Week 4), and End of Treatment (Week 8) Visits.

Food Reward: Food reward will be assessed by exposing participants to 16 computer-based images of common snack foods spanning caloric content and macronutrient composition (low/high fat sweet, low/high fat savory). After each 5-second snack food exposure, participants

CONFIDENTIAL

This material is the property of the University of Pennsylvania. Do not disclose or use except as authorized in writing by the study sponsor

will provide ratings of how much they like the food and how pleasant it would be to eat this food right now. Ratings will be made on visual analog scales anchored by 0 (not at all) to 100 (extremely). The food reward task will be administered at the Baseline (Week -2), Mid.-Tx 1 (Week 1), Mid.-Tx 3 (Week 4), and End of Treatment (Week 8) Visits.

Food Reinforcement (RRVF): The Relative Reinforcing Value of Food will be assessed via a validated behavioral choice task, permitting the evaluation of the preference for food over other alternatives. Participants will be asked to move a computer mouse to hit targets on one of two sides of a split-screen monitor, to earn points toward either food or money. Participants selected the snack food (salty or sweet) that they wanted to consume for the assessment at the Intake Visit. Using a concurrent schedule, participants will be told that they can switch from working on one side of the screen to the other as often as they wish. Adapted from previous research, participants will be instructed to move the computer mouse to have the cursor hit the targets (either a \$ or food). Consistent with relative reinforcement paradigms, the reinforcement schedule in the money-earning screen will remain constant at a fixed ratio FR-25 (25 targets achieved to earn a point) while the reinforcement schedule for food will increase (require more effort) with a progressive ratio schedule of PR-25x over 10 trials, such that 25, 50, 75, 100, 125, 150, 175, 200, 225, and 250 targets will have to be achieved to earn a point. The computer task will be performed until a participant completes 10 trials and accumulates a total of 10 points from which they will earn either \$0.10 for each point (i.e., up to \$1.00 paid at the end of the task) or a standardized amount (grams) of their chosen snack food for each point. Food earned is consumed at the end of the task to prevent satiation from influencing responding in subsequent trials. Participants will then begin a 30-minute wait period to standardize session duration and ensure that responding is based on reinforcer preference. At the discretion of the research staff, participants who become frustrated with the length of the RRVF task may bypass the 30-minute wait period. Per convention, the RRVF outcome is defined by a breakpoint (maximum amount of responding) for food vs money across the trials. The Relative Reinforcing Value of Food behavioral choice task will be administered at the Baseline (Week -2), Mid.-Tx 1 (Week 1), Mid.-Tx 3 (Week 4), and End of Treatment (Week 8) Visits.

Alternative Reinforcers (freq, enjoy) (PES): Alternative reinforcers will be measured by the adapted Pleasant Events Schedule, designed to assess reinforcers that occur in the natural environment. The 78 items are rated once in terms of frequency (0 = none to 2 = often) and once in terms of enjoyability (0 = none to 2 = very) over a specified number of days, yielding a *frequency* score, an *enjoyability* or subjective reward score, and the cross product is the reinforcement from the activity. This measure differentiates among smoking and treatment-seeking status, is sensitive to changes in reinforcers across smoking cessation treatment, and has been used to assess reinforcers in substance abusers. Alternative reinforcers (PES) will be measured at the Baseline (Week -2), Mid.-Tx 1 (Week 1), Mid.-Tx 2 (Week 2), Mid.-Tx 3 (Week 4), and End of Treatment (Week 8) Visits.

